4.2 METHOD OF TREATMENT ASSIGNMENT AND BLINDING

The randomization of patients will be managed by a central Interactive Voice and Web Response System (IxRS) through use of a dynamic hierarchical algorithm which includes a random component. The treatment assignments will be unblinded to selected Sponsor personnel to facilitate ongoing monitoring of safety and tolerability, including members of the IMC and SOC.

All patients will be randomly assigned to receive 3600 mg MHAA4549A, 8400 mg MHAA4549A, or placebo at a 1:1:1 ratio stratified by country, whether patient is on PPV versus supplemental O₂ at randomization, and whether the patient has suspected or

confirmed bacterial pneumonia vs no bacterial pneumonia at randomization. Initially GV29216 randomly assigned patients to receive either 3600 mg MHAA4549A, or placebo at a 1:1 ratio. The updated randomization scheme takes into account the numbers already allocated to these two arms and strata prior to allocating to the three arm design so that by the end of the study there will be an approximate 1:1:1 allocation between the three arms.

All patients will receive oseltamivir (as described in [Table 2](#)) for a minimum of 5 days. Treatment for longer than 5 days is permitted based on local investigator discretion.

Unblinded personnel (i.e., unblinded site pharmacist or other designated, qualified unblinded study personnel) at each study site will prepare the IV infusions of study drug, as described in [Section 4.3.3](#). The Sponsor will provide masking bags and blinded study personnel will administer the study drug. The other parties who are involved in the conduct of the study (i.e., patients and blinded site personnel) will remain blinded to patient-specific treatment assignments until the final database lock after the completion of the study.

Bioanalytical laboratory personnel responsible for performing PK assays will be unblinded to patients' treatment assignments to identify appropriate PK samples to be analyzed. Samples from patients assigned to the comparator arm will not be analyzed except by request (e.g., to evaluate a possible error in study drug administration).

While PK samples must be collected from patients assigned to the comparator arm to maintain the blinding of treatment assignment, PK assay results for these patients are generally not needed for the safe conduct or proper interpretation of this trial.

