6.1 DETERMINATION OF SAMPLE SIZE

The purpose of this study is estimation of the effect size and hypothesis generation regarding the effect of MHAA4549A on the time to normalization of respiratory function relative to the standard of care rather than hypothesis testing. Point and interval estimates will be obtained. Approximately 330 patients will be enrolled. It is assumed that the median time to normalization of respiratory function in the control arm is 5 days. This sample size (approximately 110 patients per arm) provides 71% power to detect a

treatment difference of 1 day for the primary endpoint in both MHAA4549A arms assuming a 2-sided alpha of 0.2 and no difference in efficacy between the two active arms. If the 3600-mg dose shows a treatment difference of 1 day and the 8400-mg dose shows a treatment difference of 1.5 days or more then this sample size provides > 86% power assuming a 2-sided alpha of 0.2.

Operating characteristics (power) under other possible assumptions for 2-sided alpha of 0.2 and true differences of 0.5 to 2 days are provided in [Table 7](#).

Table 7 Operating Characteristics for Proposed Study Design for Several Possible True Underlying Median Values

	True Underlying Median for MHAA4549A							
	3600	8400	3600	8400	3600	8400	3600	8400
	mg	mg	mg	mg	mg	mg	mg	mg
	4 days	4 days	4 days	3.5 days	4 days	3 days	4.5 days	4 days
Hazard Ratio	0.8	0.8	0.8	0.7	0.8	0.6	0.9	0.8
Power of log-rank test ^a	71.4%		86.6%		98.8%		56.2%	

Note: Operating characteristics are based on the following assumptions: 330 evaluable patients, event times are exponentially distributed, median time to normalization of respiratory function in the control arm is 5 days, and patients are followed for 60 days.

^a Two-sided $\alpha = 0.20$.

It should be noted that the study is underpowered for detection of minimally clinically meaningful differences at a 2-sided alpha of 0.05 such as a true hazard ratio of 0.80 in both MHAA4549A arms.

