6.4 EFFICACY ANALYSES

The primary and secondary efficacy analyses will include all randomized patients who are confirmed to be influenza A infected, with patients grouped according to the treatment assigned at randomization.

Time to event data will be *analyzed* using Kaplan-Meier methodology and stratified Cox proportional hazards models and will be summarized using n, median when estimable, hazard ratios, and 95% confidence intervals. Patients who are lost to follow-up (while event free) will be censored at the time that they are last known to be event free.

The ordinal outcomes will be analyzed using a proportional odds model. To supplement the overall summary odds ratio, separate odds ratios will be estimated for each dichotomized definition of improvement that can be formulated from the components of the ordinal outcome. A test for the proportionality assumption will also be made. Patients discharged from the hospital to a rehabilitation facility will be included in category 5. Patients discharged from the hospital to a nursing home will also be included in category 5, unless the patient lived in a nursing home prior to admission to the hospital, in which case the patient will be characterized based on resumption of normal activities.

Estimation of the treatment difference of proportions and *the corresponding* 95% confidence intervals will be calculated using stratum-adjusted Mantel-Haenszel methodology (Koch et al. 1989). For continuous endpoints, Analysis of Covariance methods (after appropriate transformation of data) will be used to estimate treatment differences and 95% confidence intervals.

Other than censoring in the time to event analyses, no other imputation for missing data will be performed.

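### The proportional odds model for clinical status names no randomization factors; fitted with treatment alone, it is conservative and loses some power if ventilation status is prognostic

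*Combined protocol and SAP*

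**What the plan says.** Section 6.4 (Efficacy Analyses, protocol Version 7) treats the endpoint types differently:

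- Time-to-event endpoints: "stratified Cox proportional hazards models".
- Differences in proportions: "stratum-adjusted Mantel-Haenszel methodology".
- Clinical status: "The ordinal outcomes will be analyzed using a proportional odds model". The section adds an overall odds ratio, separate odds ratios for each dichotomy of the scale, a test of proportionality, and rules for classifying patients discharged to rehabilitation or a nursing home. It names no covariate or stratum.
- Continuous endpoints: analysis of covariance, also with no covariate named.

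Section 4.2 assigns patients "at a 1:1:1 ratio stratified by country, whether patient is on PPV versus supplemental" oxygen, and by suspected or confirmed bacterial pneumonia versus none. It uses a "dynamic hierarchical algorithm which includes a random component".

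Section 6 leaves further analysis details to a separate SAP and says that there will be no formal hypothesis testing. Section 6.1 describes the aim as estimation, with point and interval estimates. The Version 7 rationale says the ordinal endpoint was added because it is expected to be more powerful than a binary outcome.

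**The concern.** The clinical-status scale runs from death through ICU, ward with oxygen and ward without oxygen to two discharged categories. Whether a patient was on positive pressure ventilation at entry bears directly on the middle of that scale. Randomization forces this factor into approximate balance between arms.

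A model that ignores a balanced prognostic factor still counts its between-patient variation as noise in the treatment comparison. Its reported standard error is then larger than the real sampling variability of its estimate. The odds ratio is also non-collapsible: the unadjusted (marginal) odds ratio lies closer to 1 than the one within strata.

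At stake are the calibration of the intervals, which are the product of an estimation study, and part of the information for which the endpoint was added. The target is also unclear: a reader cannot tell whether the reported odds ratio is meant to be marginal or conditional.

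**Working it through.** **The plan's own figure.** The documents give no power, odds ratio or alpha for the ordinal endpoint. The only power figures, in Section 6.1 and Table 7, concern the primary endpoint. The first column (medians 4 v 5 days, HR 0.8, two-sided 0.20) states 71.4%. For pooled active v placebo with 330 events and one third on placebo, Schoenfeld's formula gives √(330 × 1/3 × 2/3) × |ln 0.8| − 1.2816 = 8.563 × 0.2231 − 1.2816 = 0.629, so power is 73.5%. Simulation gives 73.0%. Both lie within about 2 points of the stated value. This confirms the reading of the sample size but says nothing about the ordinal endpoint.

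**Inputs from the documents.** "Approximately 330 patients will be enrolled", 1:1:1, so 330/3 = 110 per arm. There are six categories. PPV is capped at (about) 45% of enrolment; no expected share is given. The 95% level is stated for the other efficacy endpoints and is assumed here for the ordinal odds ratio.

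**Inputs assumed.**
- Category distributions, worst to best: Day 7, 6/14/20/20/25/15%; Day 30, 10/4/4/5/30/47%.
- Treatment odds ratio within strata: 1.5–2.0.
- PPV share 10–45%, PPV odds ratio 1–8.
- Pneumonia share 30–40%, odds ratio 1–2.5.
- Allocation balanced within PPV × pneumonia strata; country not modelled.

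**Method.** 1,500–4,000 simulated trials per scenario, each fitted by a proportional odds model without and with the two factors.

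**Results for 110 v 110, Day 30 distribution, within-stratum odds ratio 1.8.** SE is the mean model-based standard error and SD the empirical one. Coverage is of the marginal odds ratio by the unadjusted 95% interval. Power is shown as unadjusted → adjusted.

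| PPV OR (share) | Marginal OR | SE unadj. | SD unadj. | Coverage | SE adj. | Power, 0.05 | Power, 0.20 |
|---|---|---|---|---|---|---|---|
| 1 (45%) | 1.800 | 0.263 | 0.269 | 95.2% | 0.263 | 63.3 → 63.7% | 84.3 → 84.4% |
| 2 (45%) | 1.766 | 0.262 | 0.260 | 95.0% | 0.265 | 58.8 → 61.5% | 82.4 → 83.6% |
| 3 (45%) | 1.729 | 0.261 | 0.248 | 96.2% | 0.268 | 54.8 → 58.9% | 80.6 → 82.4% |
| 4 (45%) | 1.686 | 0.261 | 0.243 | 96.6% | 0.271 | 52.2 → 59.2% | 78.6 → 82.1% |
| 6 (45%) | 1.635 | 0.260 | 0.232 | 97.4% | 0.275 | 47.9 → 58.6% | 75.3 → 81.0% |
| 8 (45%) | 1.589 | 0.259 | 0.222 | 98.0% | 0.279 | 41.5 → 57.1% | 72.6 → 80.1% |
| 4 (10%) | 1.753 | 0.262 | 0.257 | 95.1% | 0.265 | 58.5 → 61.6% | 82.1 → 83.4% |

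**Hand check of the PPV OR 6 row.**
- Coverage = 2Φ(1.96 × SE/SD) − 1 = 2Φ(1.96 × 0.260/0.232) − 1 = 2Φ(2.197) − 1 = 97.2% (simulated 97.4%).
- Power = Φ((ln OR − z × SE)/SD). Unadjusted: (0.492 − 1.96 × 0.260)/0.232 = −0.08, so 47% (simulated 47.9%).
- Adjusted, with empirical SD 0.276: (0.588 − 1.96 × 0.275)/0.276 = 0.18, so 57% (simulated 58.6%).
- Interval width on the log scale: 2 × 1.96 × 0.260 = 1.02 unadjusted; 2 × 1.96 × 0.275 = 1.08 adjusted. The adjusted interval is slightly wider. The gain comes from ln 1.8 = 0.588 against ln 1.635 = 0.492.

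**Day 7 distribution, 110 v 110.** With PPV odds ratio 4–8 and 45% on PPV, SE is about 0.24 against SD 0.20–0.23, coverage is about 96–98.5%, and null rejection at nominal 5% is 2–4%. Adjusted SEs are 0.239–0.248 against 0.239–0.243 unadjusted.

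**Gain from adjustment over all scenarios, including 110 v 220, at two-sided 0.05.**
- Factors not prognostic: about 0 points.
- PPV OR 2: 1–3.
- PPV OR 3, or OR 4 with 10% on PPV: 2–4.
- PPV OR 4 with 20–45% on PPV: 4–8.
- PPV OR 6: 10–11.
- PPV OR 8: 10–16.

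At 0.20 the gain is about 0–6 points, except in the strongest scenario (3–11).

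**Sensitivity to the category distribution.** With 3/7/15/15/30/30% in the oxygen stratum at Day 7 and treatment odds ratio 1.8, 1,000 trials per scenario gave 65.5% v 71.8% at PPV OR 3 and 56.1% v 68.1% at PPV OR 6.

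**The case against.** The text is silent; it does not exclude covariates. Section 6 defers detail to an SAP that is not among the pages available here, so a reader who infers that the plan has chosen an unadjusted analysis goes too far. That stands: this is an under-specification. But Section 6.4 already settles finer matters for this endpoint, such as nursing-home discharges, and the adjustment set decides what the odds ratio means.

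A reader might also infer that the ordinal model is the only unstratified method in the section. It is not: the analysis of covariance names no factors either. The contrast holds only with the Cox and Mantel-Haenszel analyses.

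The study is estimation-only, states no power for this endpoint, and any error is on the safe side. So no planned power is lost and false positives are not inflated. The documents also do not show that omitting covariates would cancel the ordinal scale's advantage over a binary outcome. Calibrated intervals still matter in an estimation study, and the endpoint was added for its information.

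Finally, the simulated allocation is tidier than the trial's. The actual algorithm is dynamic with a random component, includes country, and moved from 1:1 to 1:1:1. Efficacy is analysed only in patients confirmed by central PCR. Each of these can loosen the balance and so reduce the over-coverage. That caveat stands.

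**Conclusion.** The point holds as a gap in specification with a conditional cost. If the model is fitted with treatment alone and PPV status is prognostic, its intervals over-cover the marginal odds ratio: about 96–98.5% for an assumed PPV odds ratio of 4–8 with 45% on PPV, and close to 95% when the factors are weak. The power given up is about 0–16 points at two-sided 0.05, and mostly 0–6 points at 0.20, the only level the plan uses for power.

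Two stronger readings are not supported. One is a fixed loss such as 6 to 12 points. That needs a PPV odds ratio of very roughly 3–6, a large PPV share and alpha 0.05; the documents give no prognostic strength, and their 45% is a ceiling, not an expectation. The other is that the intervals are simply too wide and that adjustment would shorten them. On the log scale the adjusted interval is as wide or slightly wider; the gain comes from a conditional odds ratio further from 1.

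This is worth correcting because adjustment costs essentially nothing if the factors turn out not to be prognostic.

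**What to change.** In Section 6.4, and in the SAP, state that:

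- the proportional odds model includes, as covariates recorded at randomization, PPV versus supplemental oxygen and bacterial pneumonia (suspected or confirmed versus none);
- the supplementary dichotomized odds ratios use the same terms;
- country is included, or pooled into regions by a stated rule if sparse;
- the reported odds ratio is conditional on these factors.

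The cost is a few lines of text. The factors are already collected for randomization. The one downside is that the odds ratio is no longer marginal, which the last item makes explicit. The text should be settled before any unblinded analysis, so that the choice of covariates cannot be questioned afterwards.

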6.4.1 Primary Efficacy Endpoint

- Median time to normalization of respiratory function.

6.4.2 Secondary Efficacy Endpoints

- *Clinical status at Days 1-7, 14, and 30 categorizing proportion of patients in each of the 6 pre-defined categories*
- Proportion of patients with clinical failure after 24 hours post-infusion of study drug
- Median time to clinical resolution of vital signs
- Hazard ratio for mortality at Day 14, Day 30, and Day 60
- Mean and median AUC of viral load

- Mean and median peak viral load
- Median duration of viral shedding in nasopharyngeal samples
- *Proportion of patients with detectable infection*
- Median duration of hospitalization
- Median duration of ICU stay
- Proportion of patients requiring antibiotics for respiratory indications during study
- Proportion of patients with influenza secondary complications
- Median duration of ventilation
- Proportion of patients who are readmitted by Day 30 and Day 60

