6.3 SUMMARIES OF TREATMENT GROUP COMPARABILITY

Demographic and baseline characteristics of the patient will be summarized for all randomized patients by treatment group by use of descriptive statistics. Baseline is defined as the last available value prior to study drug administration.

During the study patient disposition, concurrent treatment, and compliance with study treatment and visits will be summarized on the safety analysis population using descriptive statistics.

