Appendix 1a Schedule of *Activities*

Notes: Unless otherwise indicated, **all assessments on Day 1 should be performed prior to study drug administration**; x's within parentheses, i.e., (x), indicate optional assessments. Please refer to Follow-up Period table for visits to be completed after patient is discharged from hospital prior to Day 60. Any screening assessments completed prior to consent as standard of care do not need to be repeated if done within the screening period. If a patient is unable to be present at the site for a follow-up visit, a telephone visit is *encouraged*.

Hospitalized Days (only to be completed while patients are hospitalized)																						
	D -2,-1	D1 (Randomization)	D2	D3	D4	D5	D6	D7	D8	D9	D10	D11-13	D14	D15-19	D20	D21-24	D25	D26-29	D30	Hospital Discharge ^a	D60 Study Completion or Early Discontinuation while hospitalized	Unscheduled
Informed consent ^b	x																					
Sponsor-approved influenza test ^c	x																					
Inclusion/exclusion criteria	x																					
Medical history and demographic	x																					

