Appendix 1a Schedule of Activities (cont.)

Hospitalized Days (only to be completed while patients are hospitalized)																						
	D -2,-1	D1 (Randomization)	D2	D3	D4	D5	D6	D7	D8	D9	D10	D11-13	D14	D15-19	D20	D21-24	D25	D26-29	D30	Hospital Discharge ^a	D60 Study Completion or Early Discontinuation while hospitalized	Unscheduled
Oseltamivir medication diary ^{dd}																				x		
Clinical status assessment ^{ee}		x	x	x	x	x	x	x					x						x			

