Appendix 1a Schedule of Activities (cont.)

- ^h Vital signs will be collected within 1 hour before MHAA4549A infusion and within 1 hour after completion of MHAA4549A infusion and include temperature, respiratory rate, heart rate, systolic blood pressure, and diastolic blood pressure. Temperature should be measured using the same methodology throughout the study and should be measured prior to administration of any antipyretic drugs. In patients who have multiple vital signs taken during any day, the most abnormal value should be recorded from that 24-hour period. Temperature, blood pressure, respiratory rate, and heart rate will be completed after the patient has been in a seated or supine position for > 5 minutes. The worst/most abnormal value from the last 24-hour period should be recorded for patients who are in the ICU.
- ⁱ APACHE scores are optional and only for patients that are in the ICU. For calculation of the screening APACHE score, the worst values in the *first* 24 hours should be used. APACHE scores are not required for study conduct or entry but should be collected if available.
- ^j Assessment to be conducted based on entry into ICU; may vary from patient to patient.
- ^k SOFA scores are *optional and* only for patients in the ICU that have available data such as PaO₂/FiO₂ (mmHg). See Appendix 7 for SOFA score calculation.
- ^l Patient should rest in a supine position for 10 minutes prior.
- ^m Patient will be a resident for at least 24 hours following administration of MHAA4549A.
- ⁿ Oseltamivir must be given for a minimum of 5 days. Treatment longer than 5 days is permitted based on the discretion of the investigator [indicated by (x)].
- ^o Complete physical examination includes evaluations of general appearance of head, eyes, ears, nose, and throat, cardiovascular, dermatological, musculoskeletal, respiratory, gastrointestinal, genitourinary, and neurological systems. Changes from any prior examination should be recorded. New or worsened abnormalities should be recorded as AEs, if appropriate. Day 1 physical examination is optional if *already completed* on Day -1 or -2.

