Appendix 12 ***Clinical Status Assessment***

Clinical status will be assessed on Days 1-7, 14, and 30. Assessment should be collected at a consistent time throughout the study. Indicate the patient's clinical status for the day:

- 1. Death;*
- 2. In the ICU;*
- 3. Non-ICU hospitalization, requiring supplemental oxygen;*
- 4. Non-ICU hospitalization, not requiring supplemental oxygen;*
- 5. Not hospitalized, but unable to resume normal activities; or*
- 6. Not hospitalized with full resumption of normal activities*

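### Day 1 clinical status is listed as an efficacy outcome although it is scheduled before dosing, and the ordinal model names no baseline or stratification term

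*Combined protocol and SAP*

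**What the plan says.** Sections 2.3, 3.3.3 and 6.4.2 and Appendix 12 of the Version 7 protocol all give the same nine time points for the six-level ordinal endpoint. Section 6.4.2 words it as "Clinical status at Days 1-7, 14, and 30 categorizing proportion of patients in each of the 6 pre-defined categories".

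The general note heading Appendix 1a says that, unless otherwise indicated, "all assessments on Day 1 should be performed prior to study drug administration". The row "Clinical status assessment" is marked on the Day 1 (Randomization) column. Its footnote (ee) only lists the six categories and makes no exception on timing. Section 6.3 adds: "Baseline is defined as the last available value prior to study drug administration".

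On the analysis, Section 6.4 says "The ordinal outcomes will be analyzed using a proportional odds model". It then asks for a separate odds ratio at every split of the scale and for a test of proportionality. No covariate or stratum is named for this model. The same section specifies "stratified Cox proportional hazards models" for time-to-event data and a stratum-adjusted Mantel-Haenszel method for proportions. Section 6 leaves further analysis detail to the SAP.

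**The concern.** A value taken before the infusion cannot respond to the infusion. If Day 1 is analysed like the other days, the report will contain an efficacy odds ratio that can only show how well randomization balanced the arms. If one model is fitted across days, which the protocol neither says nor excludes, Day 1 would dilute the summary odds ratio.

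Day 1 status is also the starting level on the same scale as the outcome, so it is a natural covariate for the later days. The Version 7 rationale added this endpoint because an ordinal outcome was expected to have more power than a binary one. Leaving out a prognostic starting level would give some of that gain away.

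**Working it through.** **1. Is Day 1 pre-dose?** The Appendix 1a note sets pre-dose as the default. Where the schedule wants something else on Day 1, it says so: footnote f puts the daily trial off oxygen after study drug, footnote h asks for vital signs before and after the infusion, and footnote y asks for a PK sample after it. Footnote ee has nothing comparable. By the Section 6.3 definition, a pre-dose Day 1 status is baseline.

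**2. Which categories can occur on Day 1?** Entry requires hospital care on oxygen or PPV (Section 3.1.1), so nearly all patients are in category 2 (ICU) or 3 (ward, on oxygen). Category 4 needs oxygen to have been weaned before dosing. Categories 5 and 6 (discharged) cannot occur, and category 1 (death) is essentially empty. Of the five splits of the scale:

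| Split | Day 1 |
|---|---|
| 1 vs 2-6 | essentially empty side |
| 1-2 vs 3-6 | estimable |
| 1-3 vs 4-6 | only if some patients are off oxygen |
| 1-4 vs 5-6 | empty side |
| 1-5 vs 6 | empty side |

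Three of the five required odds ratios cannot be estimated, and the six-level model is close to a binary ICU comparison.

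**3. What does a Day 1 comparison return?** With 110 per arm, an assumed 35% in ICU in both arms and 4,000 simulated trials, it rejects in 5.2% of trials at alpha 0.05 and 19.3% at alpha 0.20. These are the nominal rates.

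**4. What does omitting Day 1 status cost on a later day?** The plan gives no power, effect size or category distribution for this endpoint, so there is no stated figure to reproduce. Inputs:

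- From the documents: 110 per arm (Section 6.1), and planning alpha 0.20 (Section 6.1, for the primary endpoint).
- Share in ICU at baseline, p: 27% or 45%. These are assumptions. The first is the share of a hospital database population that needs ICU admission (Section 3.2.2). The second is the cap on PPV patients (Section 3.1.1). Neither is Day 1 ICU occupancy.
- Assumed: conditional treatment odds ratio 1.8; later-day control distribution, categories 1 to 6, of 0.03, 0.10, 0.17, 0.15, 0.35, 0.20; baseline odds ratio OR_B of 1, 3, 6 or 10 for worse status if in ICU on Day 1.

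Model, with T = 1 for active and B = 1 for ICU at baseline:

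logit P(Y ≤ k) = α_k − log(1.8)·T + log(OR_B)·(B − p)

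Each simulated trial (two arms, 1,000 per row and alpha) was fitted with T alone and with T and B. Power in %, loss in points:

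| p | OR_B | 0.05: T | T + B | loss | OR, T alone | 0.20: T | T + B | loss |
|---|---|---|---|---|---|---|---|---|
| 27% | 1 | 68.5 | 68.2 | −0.3 | 1.80 | 88.8 | 88.7 | −0.1 |
| 27% | 3 | 65.4 | 68.5 | 3.1 | 1.77 | 84.6 | 85.7 | 1.1 |
| 27% | 6 | 59.9 | 68.3 | 8.4 | 1.71 | 79.8 | 86.1 | 6.3 |
| 27% | 10 | 52.5 | 69.2 | 16.7 | 1.64 | 77.6 | 86.8 | 9.2 |
| 45% | 1 | 68.4 | 68.6 | 0.2 | 1.81 | 87.5 | 87.4 | −0.1 |
| 45% | 3 | 64.7 | 69.8 | 5.1 | 1.76 | 84.4 | 86.9 | 2.5 |
| 45% | 6 | 54.6 | 66.1 | 11.5 | 1.66 | 79.4 | 86.6 | 7.2 |
| 45% | 10 | 49.8 | 65.6 | 15.8 | 1.61 | 72.4 | 84.2 | 11.8 |

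The odds-ratio column is from the alpha 0.05 runs; with B in the model it is 1.80 to 1.83 throughout. Monte Carlo error on one power is about √(0.6 × 0.4 / 1000) = 1.5 points. Both models see the same trials, so the losses are more precise than that.

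**The case against.** **Timing.** The pre-dose reading is an inference from a general note. The adverse-event row is also marked on Day 1 without a footnote, although routine adverse-event reporting starts only after study drug (Section 5.3.1), so a missing exception is not proof. Appendix 12 asks for the status for the day and says "Assessment should be collected at a consistent time throughout the study", without mentioning dosing. This leaves some ambiguity about clock time, but nothing there overrides the note. A post-dose reading would not help much either: "Patient will be a resident for at least 24 hours following administration of MHAA4549A", so the discharged categories stay empty on Day 1.

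**Adjustment.** A reader might infer that Section 6.4 prescribes an unadjusted model. It does not. It names a model and is silent on covariates, and it does not list the Cox or Mantel-Haenszel strata either. Detail is deferred to the SAP, and the part of the document reviewed contains no SAP text. This stands: the protocol names no adjustment, which is not the same as ruling one out.

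**Criterion.** Section 6 says there is no formal hypothesis testing, and Section 6.1 describes the aim as estimation, with a planning alpha of 0.20. Power at 0.05 is therefore only a yardstick for precision, and the losses at 0.20 are smaller.

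**Bias.** A reader might take the shift of the odds ratio toward 1 as bias. Treatment is randomized, so this is non-collapsibility: the unadjusted model validly estimates a marginal odds ratio.

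**Balance.** Randomization is stratified by PPV and bacterial pneumonia through a dynamic algorithm, which should restrain Day 1 imbalance. That lowers the chance of a misleading Day 1 result, but it does not turn Day 1 into an outcome, and the reported interval for later days does not benefit unless the factors are in the model. PPV and Day 1 status may overlap in part.

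**Presentation.** Section 6.4.2 could be read as tabulating category proportions over time, with Day 1 as the starting point. That use is unobjectionable, but the text does not limit Day 1 to it.

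**Conclusion.** The concern holds in a limited form. On the current text, Day 1 status is named as an efficacy outcome while meeting the protocol's own definition of baseline. A Day 1 odds ratio cannot show a treatment effect, and most of its required splits cannot be estimated. That part rests on the wording alone and needs no simulation.

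The second part is conditional. If no baseline term is added in the SAP and Day 1 status is prognostic, the later-day estimates lose precision. The range runs from nothing to 16 to 17 points of power at alpha 0.05, and to 9 to 12 points at alpha 0.20, depending on a baseline odds ratio that the documents do not give. It would be wrong to read any one row of the table as the trial's expected loss. With no formal testing, the practical effect is a less informative estimate on one secondary endpoint. The primary endpoint and the sample size are not affected.

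**What to change.** - In Sections 2.3, 3.3.3 and 6.4.2 and Appendix 12, define the ordinal outcome on Days 2-7, 14 and 30 (eight post-dose time points). Keep the Day 1 assessment, state that it is pre-dose, and report it with the baseline characteristics in Section 6.3.
- In Section 6.4 and the SAP, specify the proportional odds model with treatment, Day 1 clinical status, PPV versus supplemental oxygen, and bacterial pneumonia as terms, and say whether it is fitted day by day or across days.

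The cost is wording only. Day 1 status and both stratification factors are already collected, and in the simulations adjustment gave essentially the same power when Day 1 status was not prognostic and more when it was.
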